7. DELAYING OR DISCONTINUING STUDY TREATMENT AND PARTICIPANT WITHDRAWAL FROM THE STUDY

7.1. Criteria for Delay of Study Treatment

Body temperature must be measured at the Day 1, Day 29, OL-D1, OL-D29, and BD-1 visits prior to any study treatment administration.

The following events constitute criteria for delay of study treatment, and if any of these events occur at the time scheduled for dosing, the participant may be injected at a later date within the time window specified in [Table 16](#), [Table 21](#), [Table 22](#), and [Table 23](#), or the participant may be discontinued from dosing at the discretion of the investigator ([Section 7.2](#)):

- Acute moderate or severe infection with or without fever at the time of dosing.
- Fever, defined as body temperature $\geq 38.0^{\circ}\text{C}$ (100.4°F) at the time of dosing.
- Part B only: Diagnosed COVID-19 by detection of SARS-CoV-2 by RT-PCR and accompanying symptoms. Participant must be asymptomatic at the time of dosing, although they may still be RT-PCR positive, with the exception of fatigue and loss of sense of smell or taste, if by the investigator's judgement these are deemed to be mild chronic sequelae.
- Part C only: Seasonal influenza vaccine that was administered within 14 days of the BD-1 visit.
- Part C only: Diagnosed COVID-19 by detection of SARS-CoV-2 by RT-PCR and accompanying symptoms after completion of the primary vaccination series in Part A or Part B. For all study participants who were confirmed to have COVID-19 infection after Dose 1 and Dose 2 of mRNA-1273 but before the booster, the BD-1 visit should be delayed for 90 days from the receipt of monoclonal Ab (mAb) or convalescent plasma (CP) if given as a part of treatment per CDC recommendations. For participants who did not receive mAb or CP, BD can be administered after a minimum of 30 days from the onset of COVID-19 symptoms and complete resolution of the acute illness (except fatigue and loss of sense of smell or taste). A delay of 90 days may be considered, if feasible. If these criteria delay the BD-1 visit date beyond the allowable window per the study timeline, the subject may not receive the dose as a part of the study.

Participants with a minor illness without fever, as assessed by the investigator, can be administered IP. Participants with a fever of 38.0°C (100.4°F) or higher will be contacted within the time window acceptable for participation and reevaluated for eligibility. If the investigator determines that the participant's health on the day of administration temporarily precludes dosing with IP, the visit should be rescheduled within the allowed interval for that visit.

7.2. Discontinuation of Study Treatment

Every reasonable attempt will be made to follow up with participants for safety throughout the entire study period, even if further dosing is discontinued or the participant misses one or more visits. Except for participants who withdraw consent or who are withdrawn from the study due to receipt of non-study COVID-19 primary series or first booster vaccine ([Section 7.3.1](#)), a participant who withdraws or is withheld from receiving the second dose of study vaccine in Part A or Part B will be considered to have discontinued treatment but will remain in the study and complete all scheduled visits and assessments ([Section 11.1](#)). Except for participants who withdraw consent or who are withdrawn from the study due to receipt of non-study COVID-19 primary series or first booster vaccine ([Section 7.3.1](#)), a participant who does not receive the BD in Part C will NOT be considered to have discontinued treatment and will remain in the study and complete all scheduled visits and assessments.

The investigator, in consultation with the Sponsor's medical monitor, may withhold a participant from further dosing if the participant experiences any of the following:

- Becomes pregnant ([Section 8.3.6](#))
- Develops, during the course of the study, symptoms or conditions listed in the exclusion criteria
- Experiences an AE (other than reactogenicity) after dosing that is considered by the investigator to be related to IP ([Section 8.3.10](#)) and is of Grade 3 (severe) or greater intensity ([Section 8.3.9](#))
- Experiences an AE or SAE that, in the judgment of the investigator, requires study IP withdrawal due to its nature, severity, or required treatment, regardless of the causal relationship to vaccine
- Experiences a clinically abnormal vital sign measurement or finding on physical examination, or general condition that, in the judgment of the investigator, requires IP withdrawal

The reason(s) for discontinuation from further dosing will be recorded in the eCRF.

Prior to receiving a second dose of study vaccine in Part A or Part B and prior to receiving a BD in Part C (as applicable), participants will be reassessed to ensure that they continue to meet eligibility requirements as outlined below.

The following events in a participant constitute absolute contraindications to any further dosing of the IP to that participant. If any of these events occur during the study, the participant must not receive additional doses of vaccine but will be encouraged to continue study participation for safety through end-of-study period as defined in [Section 4.4](#).

- Part A only: Diagnosed COVID-19 by detection of SARS-CoV-2 in a Day 1 NP swab sample or COVID-19 diagnosed prior to Day 29. If COVID-19 is suspected on or prior to Day 29, further administration of IP must be withheld until COVID-19 test results are available.
- Anaphylaxis or systemic hypersensitivity reaction following the administration of vaccine.
- Any SAE judged by investigator or Sponsor to be related to study vaccine.
- Any clinically significant medical condition that, in the opinion of the investigator, poses an additional risk to the participant if he/she continues to participate in the study.

7.3. Participant Withdrawal From the Study

7.3.1. Participant Withdrawal

Participants who withdraw from the study will not be replaced. A “withdrawal” from the study refers to a situation wherein a participant does not return for the final visit planned in the protocol. The statistical management of participant withdrawals is discussed in [Section 9](#).

Participants can withdraw consent and withdraw from the study at any time, for any reason, without prejudice to further treatment the participant may need to receive. The investigator will request that the study participant complete all study procedures pending at the time of withdrawal.

A participant who withdraws consent or who is withdrawn from the study may request destruction of any samples taken and not tested, and the investigator must document this in the site study records. If the participant withdraws consent for disclosure of future information, the Sponsor may retain and continue to use any data collected before such a withdrawal of consent (see [Section 11.2.10](#)).

The Sponsor will continue to retain and use all research results that have already been collected for the study evaluation, unless the participant has requested destruction of these samples. All biological samples that have already been collected may be retained and analyzed at a later date (or as permitted by local regulations).

If participant desires to withdraw from the study because of an AE, the investigator will try to obtain agreement to follow up with the participant until the event is considered resolved or stable and will then complete the end of study eCRF.

Information related to the withdrawal will be documented in the eCRF. The investigator will document whether the decision to withdraw a participant from the study was made by the participant or by the investigator, as well as which of the following possible reasons was responsible for withdrawal:

- AE (specify)
- SAE (specify)
- Death
- Lost to follow-up (LTFU)
- Physician decision (specify)
- Pregnancy
- Protocol deviation
- Study terminated by Sponsor
- Withdrawal of consent by participant (specify); this includes participants who, at the PDV, withdraw consent from continuing in the study.
- Other (specify)

Participants who are withdrawn from the study because of AEs (including SAEs) must be clearly distinguished from participants who are withdrawn for other reasons. Investigators will follow up with participants who are withdrawn from the study as result of an SAE or AE until resolution of the event.

Participants who are confirmed to have received placebo upon unblinding and intend to receive a COVID-19 vaccine either licensed or under an EUA outside of this study will be withdrawn from the study. In addition, any participant confirmed to have received or plans to receive a non-study COVID-19 vaccine for their primary series or first booster only, either licensed or under EUA, will be withdrawn from the study. If a participant has an ongoing AE or pregnancy at the time of receipt of a non-study COVID-19 primary series or first booster vaccine, the participant will remain in the study to allow follow-up until the resolution of the event. Participants receiving a second or subsequent non-study COVID-19 boosters will remain in the study and follow all study procedures.

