In addition, any participant confirmed to have received or plans to receive a non-study COVID-19 vaccine, either licensed or under EUA, may also not be included in the PP analysis (and may also be withdrawn from the study per [Section 7.3.1](#) if non-study COVID-19 vaccine is primary series or first booster).

If a participant takes a prohibited drug therapy, the investigator and the CRO's medical monitor will make a joint decision about continuing or withholding further dosing from the participant based on the time the medication was administered, the drug's pharmacology and pharmacokinetics, and whether use of the medication will compromise the participant's safety or the interpretation of data. It is the investigator's responsibility to ensure that details regarding the concomitant medications are adequately recorded in the eCRF.

All medication and interventions necessary for the appropriate care for the study participant, particularly to treat COVID-19, should be administered and appropriately documented along with the AE.

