5.1.5. Analysis Periods

Analysis periods and treatment groups for analysis of Part B, Part C, and Primary Series are summarized in Table 1. For effectiveness, participants will be included in treatment groups based on ‘as-planned’ or ‘intent-to-treat’ assignments; for safety, participants will be included in treatment groups based on ‘as treated’ groups (treatment actually received), details are provided to Appendix F. For analysis of immunogenicity, ‘per-protocol’ sets will be used as analysis population and ‘per-protocol’ sets require participants receiving planned treatments.

Table 1 Analysis Periods for Analyses of Part B, Part C, and Primary Series

Treatment Group/Cohort	Description	Analysis Period
Part B (Effectiveness)		
mRNA-1273	Participants randomized to mRNA-1273 in the Blinded Phase Date of reference: PDV/unblinding	From PDV/unblinding to earlier date of (BD-1 visit, DBL or data cutoff date for efficacy, last observed in study ^a)
Placebo	Participants randomized to Placebo in the Blinded Phase and did not request to receive mRNA-1273 in Part B Date of reference: Dose 1 of mRNA-1273	
Placebo-mRNA-1273	Participants randomized to Placebo in the Blinded phase and requested to receive mRNA-1273 in Part B Date of reference: Dose 1 of mRNA-1273 in Part B	
Part B (Safety)		
mRNA-1273	Participants received at least one dose of mRNA-1273 in the Blinded Phase	From PDV/unblinding or 1 st dose of mRNA-1273 in Part B to earlier date of (BD- Day 1, DBL or data cutoff date for safety, last observed in study ^a).
Placebo	Participants only received Placebo in the Blinded Phase and did not receive mRNA-1273 in Part B	
Placebo-mRNA-1273	Participants only received Placebo in the Blinded phase and received mRNA-1273 in Part B	
Part C (Effectiveness, Immunogenicity, Safety)		
Booster 50 µg after mRNA-1273 primary series	Participants randomized to/received mRNA-1273 in the Blinded Phase and received booster 50 µg in Part C Date of reference: date of booster	From dose date in Part C to earlier date of (DBL or data cutoff date for safety, last observed in study ^a).

Booster 50 µg after Placebo-mRNA-1273 Primary Series	Participants randomized to /only received Placebo in the Blinded Phase and received at least one dose of mRNA-1273 in Part B and received booster 50 µg in Part C Date of reference: date of booster	

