Booster 50 µg	Participants randomized in the blinded phase and received booster 50 µg in Part C Date of reference: date of booster	From dose date in Part C to earlier date of (DBL or data cutoff date for safety, last observed in study ^a).
Not received booster	Participants randomized to/received mRNA-1273 in Part A or B and did not receive booster in Part C Date of reference: date of BD-visit 1	Up to earlier date of (DBL or data cutoff date for safety, last observed in study ^a).
Placebo	Participants randomized to/only received Placebo in Part A or B and did not receive booster in Part C Date of reference: date of BD-visit 1	From BD-visit 1 in Part C to earlier date of (DBL or data cutoff date for safety, last observed in study ^a).
Effectiveness, Immunogenicity of mRNA-1273 primary Series		
mRNA-1273	Participants randomized to mRNA-1273 in the Blinded Phase	From Dose 1 of mRNA-1273 to earlier date of (booster date, DBL or data cutoff date, last observed in study ^a).
Placebo-mRNA-1273	Participants randomized to Placebo and received mRNA-1273 in Part B	
Safety of mRNA-1273 primary Series		
mRNA-1273	Participants received mRNA-1273 in the Blinded Phase	From Dose 1 of mRNA-1273 to earlier date of (booster date, DBL or data cutoff date, last observed in study ^a).
Placebo-mRNA-1273	Participants received Placebo in the Blinded phase and received mRNA-1273 in Part B	

^a last observed in study is the earliest date of study discontinuation, study completion, or death.

All analyses will be conducted using SAS Version 9.4 or higher unless otherwise specified.

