In the Part C booster dose phase of the study, all participants will have scheduled blood sample collected at BD Day 1 visit. NP swab test at this visit is optional. Participants who received the booster dose of mRNA-1273 in Part C will have blood sample collected at BD Day 29 and BD Day 181 (6 months post-booster). For Part C, subjects with early infection, as detected by positive RT-PCR at scheduled visits, or positive bAb against SARS-CoV-2 nucleocapsid protein at the scheduled visits, will be censored at the time of early infection. If a participant had eligible symptom(s) within 14 days of positive RT-PCR at scheduled visits, the participant is considered to be a case for COVID-19.

Subjects who have no documented COVID-19 will be censored at the earlier date of DBL or data cutoff date for efficacy, date of last observed in study defined as the earlier of study completion date, early discontinuation date from study, or date of death. For analysis of Part B or primary series, subjects who have no documented COVID-19 will be censored at the earlier date of date of booster, DBL or data cutoff date for efficacy, or date of last observed in study defined as the earlier of study completion date, early discontinuation date from study, or date of death.

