5.3.1.2. Analysis approach for effectiveness of vaccine

COVID-19 will be evaluated using incidence rates. Number of events and incidence rate will be provided in a dynamic approach for each treatment cohort, e.g., a participant without COVID-19 or SARS-COV-2 infection will no longer be considered as “at risk” in the non-booster treatment group from the timepoint when this participant received the booster dose, instead, this participant will be considered as “at risk” in the booster treatment group from that timepoint. Incidence rate will be calculated as the number of

participants with an event divided by the number of subjects at risk adjusted by person-time (years) in each treatment cohort.

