5.6.1.1. Methods Proposed by Tsiatis and Davidian (2021a/b)

Tsiatis and Davidian (2021a/b) proposed a framework to conceptualize counting process for infection by making transparent assumptions about biological, behavioral and other phenomena. The method provides a mechanism based on inverse probability weighting (IPW) to account for possible confounding. The confounding is introduced in the process of unblinding and post-treatment choice of cross-over to vaccine for those who are originally assigned to placebo.

In this approach, the VE is modeled via the following infection rate ratio

$$R^b(\tau; \theta) = \exp\{\zeta(\tau)\}I(\tau < \ell) + \exp\{\theta_0 + g(\tau - \ell; \theta_1)\}I(\tau \geq \ell) \quad (1)$$

and $VE=1-R^b(\tau; \theta)$

Here, τ is the time since vaccination, and ℓ is the lag time from vaccination to full immunity achieved, which is approximately 6 weeks (2 doses given 28 days apart, and 14 days for vaccine effect to ramp up) The relevant VE is therefore estimated by two parts:

- The first part is via θ_0 , which models the VE at the time when full immunity is achieved ($\tau = \ell$). This is mainly estimated via the data from double-blind period where the infection data from both vaccine arm and placebo arm is available.
- The second part is via θ_1 , which models the waning effect as a function of time since vaccination. $\theta_1 = 0$ implies that VE doesn't change with time since vaccination, and $\theta_1 > 0$ implies that VE decreases with increased time since vaccination, meaning waning. And the value of θ_1 indicates the magnitude of waning effect. We will explore different optional form of the g function (e.g. linear, or piece-wise constant) to evaluate how the effect change over time.
 - The data from unblinded phase will contributing in estimating the waning effect θ_1 , by evaluating how infection rates changes under vaccine arm after different times since vaccination τ_1 and τ_2 . The infection rates can be estimated based on the infection status data at time t from vaccinated individuals who received vaccine at times $t - \tau_1$ and $t - \tau_2$, respectively.

This will reflect information about waning of the vaccine itself while controlling for the possibly different background infection rate at time t .

Data will be censored at the time of booster.

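### Part C booster follow-up is not censored at a further non-study COVID-19 vaccine, so the booster effectiveness estimates can mix in another dose

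*Protocol*

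**What the plan says.** Protocol 7.3.1 has two rules for non-study vaccines. The first: any participant who has had, or intends to have, a "non-study COVID-19 vaccine for their primary series or first booster only, either licensed or under EUA, will be withdrawn from the study". Someone with an ongoing AE or pregnancy at that moment is kept until the event resolves. The second covers later doses: "Participants receiving a second or subsequent non-study COVID-19 boosters will remain in the study and follow all study procedures".

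Protocol 6.4.3 adds that any recipient of a "non-study COVID-19 vaccine, either licensed or under EUA, may also not be included in the PP analysis".

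In the SAP for Parts B and C, Table 1 (5.1.5) sets the Part C period for boosted participants as "From dose date in Part C to earlier date of (DBL or data cutoff date for safety, last observed in study"), and its footnote reads: "last observed in study is the earliest date of study discontinuation, study completion, or death". Section 5.3.1.1 agrees: "Subjects who have no documented COVID-19 will be censored at the earlier date of DBL or data cutoff date for efficacy", or at the last-observed date. It adds the booster date as an end point only for Part B and the primary series. For Part C it also censors at infection found at a scheduled visit by RT-PCR or nucleocapsid antibody.

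Under the dynamic risk set in 5.3.1.2, a person who is boosted leaves the non-booster group, and "this participant will be considered as “at risk” in the booster treatment group from that timepoint". No further move is described. For the primary-series durability model in 5.6.1.1: "Data will be censored at the time of booster".

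**The concern.** The SAP ends follow-up for the primary series when the next dose arrives, because what happens afterwards belongs to that dose. It does not apply the same principle to the study booster, although the protocol expects some participants to take another vaccine and stay in. A person who takes a second, non-study booster goes on contributing person-time and cases to the study booster.

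Four outputs are exposed: incidence after the booster, its pattern over time, the boosted-versus-unboosted contrast (5.3.1.2.3 and the 5.6.2 models), and the BD-Day 181 antibody summaries. Durability is the most sensitive, because further doses accumulate late and could hide waning.

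**Working it through.** The documents give no sample size, event count or power for booster effectiveness, and no uptake of further doses, so there is no planned figure to reproduce. The check is textual, followed by an illustration.

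**Where follow-up ends**

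| Analysis | Stops at the next dose? | Source |
|---|---|---|
| Primary series, incidence | Yes, at the booster | SAP Part B/C Table 1; 5.3.1.1 |
| Primary series, durability model | Yes, at the booster | 5.6.1.1 |
| Boosted group, incidence | No | Table 1; 5.3.1.1 |
| Booster models | No term for a further dose | 5.6.2.1; 5.6.2.2 |
| Not received booster group | No SAP rule; a non-study first booster normally ends follow-up through withdrawal | Table 1; Protocol 7.3.1 |

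1. *Boosted group.* Staying in the study is not discontinuation, so the last-observed date is not triggered by a further dose. Person-time runs on, and a case in it counts as an event.
2. *Unboosted group.* Most recipients of a non-study first booster are withdrawn. Those kept for an ongoing AE or pregnancy remain in the Not received booster group.
3. *Exclusion route.* Part C PPS (4.5) drops major deviations that the sponsor settles before database lock (5.2.6). Neither section names this event. If used, the exclusion removes the whole participant because of something that happened after the booster.

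**Illustrative size.** All inputs here are assumptions. Let E be the effectiveness of the study booster alone, f the share of boosted person-time after a further dose, and r the case-rate ratio after versus before that dose.

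Boosted incidence is multiplied by 1 − f(1 − r). Apparent effectiveness = 1 − (1 − E)(1 − f(1 − r)).

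- Incidence is understated by 0.10 × 0.20 = 2% at the low end (f = 10%, r = 0.8) and by 0.30 × 0.60 = 18% at the high end (f = 30%, r = 0.4).
- E = 50%, f = 10%: 1 − 0.5 × 0.98 = 51% (r = 0.8) to 1 − 0.5 × 0.94 = 53% (r = 0.4).
- E = 50%, f = 30%: 1 − 0.5 × 0.94 = 53% to 1 − 0.5 × 0.82 = 59%.
- Late interval, E = 20%, f = 50%: 1 − 0.8 × 0.90 = 28% to 1 − 0.8 × 0.70 = 44%.

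**Opposite direction.** Let a share h of unboosted person-time follow a non-study first booster with rate ratio q. Then apparent effectiveness = 1 − (1 − E)(1 − f(1 − r)) / (1 − h(1 − q)).

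- With f = 0, h = 4%, q = 0.5, E = 50%: 1 − 0.5/0.98 = 49.0%.
- The two effects cancel when f(1 − r) = h(1 − q), for example 0.10 × 0.20 = 0.04 × 0.50.
- If takers of a further dose have a higher case rate than before it, say r = 1.2 at f = 10%: 1 − 0.5 × 1.02 = 49%.

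**Titers.** BD-2 is due 28 days after the booster, window −3/+14, so 25 to 42 days. BD-3 is due at 180 ± 14, so 166 to 194 days. Non-study vaccines within 28 days of a dose are restricted (Protocol 5.1.2 and 6.4.3). A further dose could therefore hardly precede BD-Day 29 samples but could precede BD-Day 181 samples, whose analysis window (SAP Appendix B) runs from Z+106 to end of study, Z being the booster date. If a share g of those samples follows a further dose that raises titers k-fold, the GMT is inflated by k^g. At g = 10% this is 1.07 to 1.23 (k = 2 to 8); at g = 30% it is 1.23 to 1.87.

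**Time available.** Protocol Amendment 9, which introduced Part C, is dated 10 Sep 2021. At the April 2022 cutoff given as an example in SAP 5.3.1.2.1, post-booster follow-up is at most 232 days (10 Sep 2021 to 30 Apr 2022). Study follow-up goes further: first doses in July to December 2020 put Day 759 (758 days later) between 29 Jul 2022 and 28 Jan 2023.

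**The case against.** The best case for the plan has five parts.

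- *The exclusion route may remove these people.* Protocol 6.4.3 permits it, and Part C PPS and the 5.3.1.2.3 comparison both have a deviation filter. This stands in part: it is undetermined whether the person-time stays in. But the rule is optional, the SAP does not name the event, and dropping whole participants on a later event discards valid earlier follow-up.
- *The bias need not favour the study booster.* A reader might infer that it does. The documents do not support that. Retained recipients of a non-study first booster lower the comparator's incidence, and people who seek a further dose are self-selected. SAP 5.6.2.2 already urges caution because booster timing is confounded, though it does not mention this event.
- *The unboosted group is largely handled.* Correct: withdrawal ends most such follow-up, and the AE and pregnancy exception is limited in time.
- *The tested immunogenicity endpoints are safe.* A reader might infer that the booster noninferiority claim is tainted. It is not, in practice: the tests use BD-Day 29. One small gap is that unscheduled samples up to Z+105 can map to that visit.
- *Retaining participants is good conduct.* Agreed. The gap is in the SAP's censoring rules, not in Protocol 7.3.1.

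In addition, model (4) in 5.6.2.2 is confined to the period between the first and last booster given, which limits its exposure.

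**Conclusion.** The gap is real. As written, Part C effectiveness follow-up and the 5.6.2 models carry on past a further non-study COVID-19 vaccine, unlike the SAP's own primary-series analyses. Unless the optional exclusion is used, person-time and cases after another vaccine count under the 50 µg booster. Post-booster incidence, durability and the boosted-versus-unboosted contrast can be distorted, and waning can be masked in late intervals.

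Size and net direction cannot be determined: the documents give no uptake, and contamination of the unboosted group works the other way. The calculated ranges rest wholly on assumed f, r, h, q, g and k. The titer problem concerns the descriptive BD-Day 181 summaries. The affected effectiveness analyses are non-randomized and outside alpha control, so no formal claim of the trial depends on this. It is worth correcting because the event is foreseen and the remedy is simple.

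**What to change.** - In SAP Part B/C Table 1 and 5.3.1.1, and in the 5.6.2 models, add a censoring date: the first non-study COVID-19 vaccine after the study booster or, in the unboosted group, after the primary series. Table 1 uses one Part C period for effectiveness, immunogenicity and safety; the new date is needed for the first two only.
- Exclude titers drawn after that date from the summaries.
- Keep each participant's follow-up before that date, and reconcile this with the optional exclusion in Protocol 6.4.3.
- Keep the uncensored version as a sensitivity analysis, because the decision to take another dose may be related to risk and the censoring may be informative.
- Confirm that dates are captured. Protocol 6.4.2 and Table 16 footnote 8 limit routine recording of non-study vaccinations to 28 days after each dose, whereas 8.3.7 has them asked about at every contact and Tables 18 and 23 schedule recording through Day 759 and BD-3.

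The cost is one extra date in the derivations and some lost person-time. No visit or retention rule changes.
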